3.2.1 Clinical Event Committee

The CEC will include at a minimum, 2 interventional cardiologists and 2 electrophysiologists. Physicians on the CEC will not participate in the study as investigators and when reviewing events will be blinded to any patient or site information. The purpose of the CEC is to adjudicate all clinical events. Specifically:

- Classify clinical events as either an Acute Coronary Syndrome (ACS) Event, a Precursor Event, or a Non Event. Non Events will be further classified as either a Transient Ischemic Event or a Non Ischemic Event. Review all deaths, and adverse events associated with diagnostic testing or procedures performed as a result of a Type I ST Episode Detection and determine relationship to system and/or procedure.
- Review all baseline surface ECGs to determine the presence or absence of any conduction abnormality.
- Review all complications and all cardiovascular related adverse events

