3.2.2 Clinical Events

ACS Events

An ACS event is defined as any of the following:

- Death due to a myocardial infarction
- A new Q-wave myocardial infarction on 12-lead ECG
- ST elevation myocardial infarction
- Biomarker evidence of acute myocardial damage*
- Evidence of new plaque rupture by invasive testing (i.e., IVUS) as adjudicated by the blinded Clinical Events Committee
- The presence of TIMI myocardial perfusion grade 0 or 1 consistent with acute injury of the myocardium from embolization
- New surface ECG ST depression or elevation treated with thrombolytic medication

Statistical Analysis Plan

- New surface ECG ST depression or elevation with new or progressive flow-limiting ischemia proven by non-invasive or invasive testing.
- Angiographic stenosis $\geq 70\%$ adjudicated by the blinded Clinical Events Committee as flow-limiting.
- An event that leads to a clinically warranted percutaneous coronary intervention (PCI) or revascularization as determined by the blinded Clinical Events Committee. Clinically warranted is defined as:
 - Angiographically visualized stenosis $\geq 70\%$ correlating with the vascular distribution in which a 12-lead surface ECG documents changes consistent with ischemia or injury in 2 or more contiguous leads
 - Angiographically visualized stenosis $\geq 70\%$ correlating with a vascular distribution shown to have ongoing ischemia by non-invasive stress testing
 - New or progressive angiographically visualized stenosis $\geq 70\%$ correlated with new or progressive anginal symptoms

*NOTE: It is recommended that the “Universal Definition of Myocardial Infarction” proposed by the Joint ESC/ACCF/AHA/WHF in 2007 be used to determine myocardial damage.

Precursor Events

A precursor event is defined as clinical symptoms of an impending ACS event followed by an ACS event within 10 days. Precursor events alone do not meet the ACS event criteria. Multiple precursor events may precede a single ACS. All precursor events will be adjudicated by the Clinical Event Committee (CEC). Symptoms identified as precursors will be grouped with the subsequent ACS event and counted as a single event. Individual precursor events will not be included in the statistical endpoint analysis.

Non Events

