Non Events are defined as any clinical event that does not meet the criteria of an ACS Event or a Precursor Event. These events will be adjudicated by the CEC and will be further classified as either Transient Ischemic Events or as Non Ischemic Events.

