3.2.3 Classification of Events

True Positive (TP): A Type I ST episode detection that occurs up to 72 hours prior to an ACS Event.

False Positive (FP): A Type I ST episode detection that occurs more than 72 hours prior to an ACS Event or that occurs in the absence of a true ACS Event.

True Negative (TN): Absence of a Type I ST episode detection during a Non Event.

False Negative (FN): Absence of a Type I ST episode detection within 72 hours prior to an ACS Event.

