4.3.2 Primary Safety Endpoint

The ST Monitoring Feature will be evaluated by the percentage of patients with false positive events. The percentage of patients with false positive events is calculated as the number of patients who experience false positives divided by the number of evaluable patients. A False Positive occurs when a clinical event does not occur within 72 hours following a Type I ST episode.

The hypothesis is formally expressed as follows:

H_0 : Percent of patients experiencing a false positive event in 12 months $\geq 15\%$

H_a : Percent of patients experiencing a false positive event in 12 months $< 15\%$

The desired outcome is to reject the null hypothesis at the 2.5% significance level. The null hypothesis will be rejected at the 2.5% significance level if the

Statistical Analysis Plan

upper bound of the 95% confidence interval for the percent of patients experiencing false positive events is less than 15%. The upper confidence bound will be calculated using the Wilson score interval method.

Patient Group

All enrolled patients who have a successful implant or system revision, complete the baseline follow up visit and have the ST Monitoring Feature and Patient Notifier turned ON will be included in the evaluation of this study endpoint. Data collection towards the study endpoint will begin after the Baseline visit.

Further, the analysis population for the primary safety endpoint will be those subjects with the Fortify[®] ST (upgraded), Fortify Assura[®] ST and Ellipse[®] ST. Data from subjects with a Fortify[®] ST device prior to being upgraded will not be included in this analysis.

Analysis

Primary Analysis

The primary analysis will be a complete case analysis where patients who are lost to follow-up before completing their 12 month visit without experiencing a false positive event will be considered non-evaluable and omitted from the analysis of the endpoint. Patients experiencing a false positive event and withdrawing before the 12 month visit will be included in the analysis. The proportion of patients experiencing false positives will be estimated by the number of patients experiencing a false positive event divided by the number of evaluable patients.

Imputation Analysis

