4.3.3 Secondary Safety Endpoint

The ST Monitoring Feature will be evaluated by the False Positive Rate (FPR). The False Positive Rate is calculated as the number of false positives per patient-year of follow-up. A False Positive occurs when there is a Type I ST episode that is not followed by a clinical event within 72 hours. Only ST segment shift events that occur beyond the baseline visit will be included in this analysis.

$$\text{FPR} = \frac{\text{\#of false positive events}}{\text{patient years of follow-up}}$$

The hypothesis is formally expressed as follows:

H₀: Expected FPR ≥ 1.9 per patient-year of follow-up

H_a: Expected FPR < 1.9 per patient-year of follow-up

The desired outcome is to demonstrate that the False Positive Rate is less than 1.9 events per patient-year. The null hypothesis will be rejected at the 2.5% significance level if the 97.5% upper confidence limit (UCL) for the expected FPR is less than 1.9 per patient-year of follow-up.

Statistical Analysis Plan

Patient Group

All enrolled patients who have a successful implant or system revision and have completed the Baseline visit with the ST Monitoring Feature and Patient Notifier programmed ON will be included in this endpoint.

Further, the analysis population for the secondary safety endpoint will be those subjects with the Fortify® ST (upgraded), Fortify Assura® ST and Ellipse® ST devices. The data from subjects with a Fortify® ST prior to being upgraded will not be included in this analysis.

Analysis

Primary Analysis

The expected FPR will be estimated by the observed FPR. To avoid imbalance in the number of false positives that each patient with false positives contributes, the maximum number of false positives from a patient that will be counted toward meeting the requirement on the number of false positives will be two. In addition, for a single follow up period (i.e. one interrogation and device evaluation to the next), if multiple false positive events occur, only one event will be counted toward the analysis. This will prevent multiple false positives that occur before the physician has the opportunity to evaluate the patient and reprogram the device from contributing to an imbalance in the data. For any patients with more than two false positives their follow up time will be truncated to the date of the second false positive.

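### The false positive rule in 4.3.2 and 4.3.3 (no clinical event within 72 hours) contradicts 3.2.3 (no ACS Event) and, as written, drops alarms followed only by a Non Event from the 15% primary safety test

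*Protocol*

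**What the plan says.** The Protocol and the SAP carry the same text on this point, so neither resolves the other.

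- **Section 3.2.3** ties the classification to ACS Events. A Type I ST episode is a true positive if it falls in the 72 hours before an ACS Event. It is a false positive if it is one "that occurs more than 72 hours prior to an ACS Event or that occurs in the absence of a true ACS Event". A true negative is "Absence of a Type I ST episode detection during a Non Event", so Non Events serve as the negative reference class.
- **Section 3.2** says that, after adjudication, every Type I ST episode is either a true or a false positive.
- **Section 4.3.2** (primary safety): "A False Positive occurs when a clinical event does not occur within 72 hours following a Type I ST episode".
- **Section 4.3.3** (secondary safety): "A False Positive occurs when there is a Type I ST episode that is not followed by a clinical event within 72 hours".
- **Section 3.2.1** gives the scope of the term through the committee's task: "Classify clinical events as either an Acute Coronary Syndrome (ACS) Event, a Precursor Event, or a Non Event". Section 3.2.2 confirms it: "Non Events are defined as any clinical event that does not meet the criteria of an ACS Event or a Precursor Event".

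The primary safety test passes if the Wilson 95% upper bound for the percentage of patients with a false positive in 12 months is below 15%.

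**The concern.** The endpoint sections use a wider class of event to excuse an alarm than 3.2.3 does. An alarm followed within 72 hours by a Non Event, and by no ACS Event, is a false positive under 3.2.3. Under 4.3.2 and 4.3.3 as written it is not. It is not a true positive either, so it falls outside a classification that 3.2 says is complete.

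The study has one arm and a fixed 15% limit, so the false positive definition decides which quantity is tested. The same alarm would count as a false positive in the positive predictive value (4.7.4) and in the preliminary assessment (4.3.1), both of which refer to 3.2.3, but not in the primary safety endpoint. A programmer who follows the endpoint section would obtain a lower percentage wherever such alarms are a patient's only false positives.

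**Working it through.** **1. The two rules side by side** (episodes detected before any event)

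| What follows within 72 hours | 3.2.3 | 4.3.2 and 4.3.3 as written |
|---|---|---|
| ACS Event | true positive | not a false positive |
| Nothing | false positive | false positive |
| Non Event only | false positive | not a false positive |

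Only the last row differs.

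**2. Direction for that row.** Suppose x of n evaluable patients have a false positive under 3.2.3, and one of them had only alarms of the last kind. Under 4.3.2 the proportion becomes (x − 1)/n if the patient completed 12 months. If the patient was lost earlier, the complete-case rule removes the patient and it becomes (x − 1)/(n − 1). Both are below x/n.

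**3. Inputs for the size.** From 4.3.2: limit 15%, one-sided 2.5%, Wilson upper bound. Not readable: the evaluable number N, the expected percentage, and f, the share of false-positive patients whose every false positive episode is followed within 72 hours only by a Non Event. N and f are therefore assumed. The sample-size text for this endpoint is blacked out, so there is no stated power to reproduce.

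**4. Largest passing count.** With z = 1.96,

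upper = [p̂ + z²/(2N) + z√(p̂(1 − p̂)/N + z²/(4N²))] / (1 + z²/N).

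For 268 of 2,000: p̂ = 0.1340, z²/(2N) = 0.00096, and the root term times z is 0.01496. Upper = 0.14992/1.00192 = 14.96%, which passes. 269 of 2,000 gives 15.02%, which fails. For N = 3,000 the limit is 411 (13.70%, upper bound 14.98%).

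**5. Chance of passing.** P(X ≤ limit), with X binomial(N, p(1 − f)) and p the true percentage under 3.2.3. The denominator is held fixed.

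At p = 15%:

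| Assumed N | f = 0 | f = 2% | f = 5% | f = 10% |
|---|---|---|---|---|
| 2,000 | 2.3% | 5.2% | 14.5% | 46.4% |
| 3,000 | 2.3% | 6.3% | 20.2% | 63.8% |

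The f = 0 column agrees with the stated 2.5% level.

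At N = 2,000 and other true percentages:

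| True 3.2.3 percentage | f = 0 | f = 5% | f = 10% |
|---|---|---|---|
| 12% | 97.4% | 99.7% | above 99.9% |
| 16% | 0.1% | 1.3% | 10.6% |
| 18% | below 0.01% | below 0.01% | 0.03% |

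The wording matters when the true percentage is near 15% and hardly at all well away from it.

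**The case against.** The strongest reply is that the rest of the text already settles the meaning. Section 4.3.1 classifies false positives by 3.2.3, and 4.7.4 uses 3.2.3 as well. Section 4.7.15 describes the 72-hour link in the primary and secondary endpoints as a link to a true ACS event. Section 4.4.1 speaks of clinical events while dividing by ACS events. This stands as evidence of intent, and loose drafting is the likely explanation. It does not remove the conflict: 4.3.2 and 4.3.3 restate the rule in full without citing 3.2.3, and no rule of precedence is given.

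A second reply also stands in part. Section 4.7.8 refers to clinical events as the study protocol defines them, and no separate definition appears in the supplied text. A narrower definition there could close the gap.

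Four stronger readings are tempting, and the documents do not support them:

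- *The endpoint wording can only favour the device.* An episode detected after ACS onset, with no later event, is not prior to the ACS Event and does not clearly meet either limb of the 3.2.3 false positive definition. As written, 4.3.2 makes it a false positive. The 3.2.3 count is at least as high only if such episodes are false positives there too. Section 3.2 implies this by elimination, but 3.2.3 does not say it.
- *Precursors open a second, longer gap.* A precursor is defined as "clinical symptoms of an impending ACS event followed by an ACS event within 10 days", so an alarm shortly before a precursor might seem excused. But 3.2.2 groups precursor symptoms with the later ACS Event as one event, and "Individual precursor events will not be included in the statistical endpoint analysis". What remains open is which onset starts the 72 hours for a grouped event.
- *The secondary test at 1.9 per patient-year would also be decided differently.* Its numerator can change, but nothing readable shows a rate near that limit.
- *The 41 events needed for the data cut-off (3.1, 4.5) include Non Events.* The sample-size text is blacked out, so this cannot be judged.

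**Conclusion.** Wrong as written. The false positive sentence in 4.3.2 and 4.3.3 contradicts 3.2.3 and leaves alarms followed only by a Non Event unclassified, contrary to 3.2. For those alarms the effect on the 15% test runs in the device's favour. No claim is made about the net direction over all episodes, because 3.2.3 does not place those detected after ACS onset.

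The size is unknown. At a true 15% with 5% of false-positive patients reclassified, the chance of passing would be 14.5% (N = 2,000) or 20.2% (N = 3,000) instead of about 2.3%. At N = 2,000 with 0 to 10% reclassified, a true 12% passes at least 97% of the time and a true 18% at most 0.03%. These figures rest on assumed N and f, on a fixed denominator, and on clinical event having the scope given in 3.2.1 and 3.2.2. The contradiction itself rests on none of the assumed numbers.

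**What to change.** - **4.3.2 and 4.3.3:** replace the false positive sentence with: *A False Positive is a Type I ST episode classified as False Positive under section 3.2.3, based on CEC-adjudicated ACS Events; an episode followed within 72 hours only by a Non Event is a False Positive.*
- **4.4.1:** in the sentence that links an event to an episode within 72 hours, change clinical event to ACS Event.
- **3.2.3:** state how an episode detected after ACS onset is classified. For an ACS Event grouped with precursors, state which onset is used for the 72-hour window.

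The cost is wording only, with no new data. The false positive percentage may be less favourable than under a literal reading of 4.3.2. The change should be made before the endpoint is programmed, so that the choice between the two rules does not depend on the results.

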4.4 Analysis of Efficacy

4.4.1 Primary Efficacy Endpoint

The efficacy endpoint will be evaluated as the sensitivity of the ST Monitoring Feature to detect clinical events. Sensitivity of the ST Monitoring Feature to detect clinical events will be calculated as the number of True Positive events (as defined in section 3.2.3) divided by the total number of ACS clinical events.

$$\text{Sensitivity} = \frac{\text{\# of TP events}}{\text{Total number of ACS events}}$$

A clinical event is considered to be related to the onset of a Type I ST episode if the clinical event occurs within 72 hours after the onset of a Type I ST episode.

The hypothesis is formally expressed as follows:

H_0 : Sensitivity \leq 50%

H_a : Sensitivity $>$ 50%

The desired outcome is to demonstrate that the sensitivity of the ST Monitoring Feature is greater than 50%. The null hypothesis will be rejected at the 2.5% significance level if the lower bound of the 95% confidence interval for sensitivity is greater than 50%. The lower confidence bound will be calculated using the Wilson score interval method.

Patient Group

All enrolled patients who have a successful implant or system revision, complete the Baseline follow up visit and have the ST Monitoring Feature and Patient Notifier turned ON, and experience clinical events will be included in the evaluation of this study endpoint. Data collection towards the study endpoint will begin after the Baseline visit.

Further, the analysis population for the primary efficacy endpoint will be those subjects with the Fortify[®] ST (upgraded), Fortify Assura[®] ST and Ellipse[®] ST devices. The data from subjects with a Fortify[®] ST prior to being upgraded will not be included in this analysis.

Statistical Analysis Plan

Analysis

Primary Analysis

The expected sensitivity for ST Monitoring Feature will be estimated by the number of true positive events divided by the total number of ACS events.

The 95% confidence limits will be calculated for sensitivity using the Wilson score interval method⁷ for a binomial proportion. The null hypothesis will be rejected if the lower bound of the 95% confidence limit is greater than 50%.

Additional Analysis

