4.7 Additional Analyses

The following additional data will be collected during the study:

- Demographic variables include: gender, age, ethnicity, cardiomyopathy classification, complete cardiovascular history, arrhythmia history, primary ICD indication, and EF% at the time of enrollment and QRS duration at baseline
- ST Diagnostic Data to include: heart rate at onset of the Type I ST episode, maximum ST shift during the Type I ST episode, Type I ST episode duration, total number of Type I ST episodes detected
- All diagnostic procedures (tests and interventions) stratified by investigator's assessment of whether the procedure would have been performed in presence and absence of ST diagnostic data

Statistical Analysis Plan

- Positive Predictive Value (PPV) of the ST Monitoring Feature
- Negative Predictive Value (NPV) of the ST Monitoring Feature
- Response rates to Patient Notifier and Merlin.net Type I ST Episode detections
- Cardiac medications (including anti-anginal medications) during clinical events
- CPK Isoenzymes, MB fractions and Troponin values collected during clinical events
- Stress test and 12-lead ECG measurements collected during clinical events
- Proportion of patients who have the ST Monitoring Feature turned off at every study visit from the Programming Visit onwards
- Adverse events
- Clinical events
- Spontaneous arrhythmic episodes
- Hospitalizations
- Mortality/Death

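### No endpoint rule responds when the ST Monitoring Feature is switched OFF after Baseline; read literally, OFF time favours the safety measures and counts against sensitivity

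*Protocol*

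**What the plan says.** The Protocol and SAP carry the same wording on every rule below.

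- **Entry, primary safety (4.3.2).** Implanted patients who "complete the baseline follow up visit and have the ST Monitoring Feature and Patient Notifier turned ON will be included in the evaluation". Section 4.4.1 sets the same condition for efficacy: patients who "have the ST Monitoring Feature and Patient Notifier turned ON, and experience clinical events will be included in the evaluation". Section 4.3.3 ties ON status expressly to the Baseline visit.
- **Evaluability, primary safety (4.3.2).** One ground only: "patients who are lost to follow-up before completing their 12 month visit without experiencing a false positive event will be considered non-evaluable". The estimate is the "number of patients experiencing a false positive event divided by the number of evaluable patients".
- **FPR (4.3.3).** Patient-years are cut short in one case only. For patients with more than two FPs, "their follow up time will be truncated to the date of the second false positive".
- **False negative (3.2.3).** "Absence of a Type I ST episode detection within 72 hours prior to an ACS Event". Nothing requires the feature to have been ON. The sensitivity denominator in 4.4.1 is all ACS events.
- **Switch-off is foreseen.** Section 4.7 lists the "Proportion of patients who have the ST Monitoring Feature turned off at every study visit from the Programming Visit onwards". Section 4.3.1 tabulates switch-off after the Programming and Baseline visits, with reasons. Neither tabulation feeds an endpoint rule.

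**The concern.** A feature that is OFF can neither raise a false alarm nor detect an ACS event. If OFF time is handled like ON time, each endpoint mixes performance of the working feature with periods when it could not perform. Applied literally, the rules have three consequences:

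- A patient switched OFF at month 2 without an FP who attends month 12 enters the denominator of the FP percentage as FP-free.
- A patient with one FP who is then switched OFF keeps adding patient-years to the FPR.
- An ACS event during OFF time has no preceding detection and is scored as a miss.

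The first two make the safety criteria easier to meet. The third lowers sensitivity and costs power. If the analyst instead treats OFF time in some other way, that choice would be made after data are seen, in a single-arm study judged against fixed margins.

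**Working it through.** **Inputs from the plan.** Safety succeeds if the Wilson 95% upper bound is below 15% (4.3.2). Efficacy succeeds if the Wilson 95% lower bound exceeds 50% (4.4.1). Both tests are at 2.5% one-sided. At least 41 events are required, and enrolment is 5,228 (Protocol 4.5).

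**Assumptions.** The documents give no switch-off rate, so the shares of 5% and 10% are illustrative. The FP hazard is constant while ON, and switch-off is unrelated to FP risk. Evaluable N is taken as 1,000 or 4,000, and true sensitivity as 70%.

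**The plan's own figure.** The design sensitivity and power are redacted, so 41 cannot be reproduced. It is plausible: under the Wilson rule with exact binomial power, 41 is the smallest number of events giving 80% power at a true sensitivity of 71%. It is not disputed here.

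**Primary safety at the null.** Let the true 12-month FP risk while ON be 15%. The risk by 6 months is 1 − √0.85 = 0.0780. If a share f goes OFF at 6 months, the counted risk is

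p = 0.15(1 − f) + 0.0780f

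The largest passing count is 127 of 1,000 (upper bound 14.91%; 128 gives 15.01%) or 555 of 4,000 (14.98%; 556 gives 15.01%). Type I error is P(Bin(N, p) ≤ limit):

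| f | counted risk p | N = 1,000 | N = 4,000 |
|---|---|---|---|
| 0 | 15.00% | 0.021 | 0.024 |
| 5% | 14.64% | 0.043 | 0.088 |
| 10% | 14.28% | 0.082 | 0.240 |

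**Primary safety beyond the null.** Let the true risk be 16%, with switch-off uniform over the year. The hazard is −ln 0.84 = 0.1744, and the mean FP risk before switch-off is 1 − 0.16/0.1744 = 0.0823. The counted risk is 0.16(1 − f) + 0.0823f. At f = 10%, 15%, 20% and 30% it is 15.2%, 14.8%, 14.4% and 13.7%. The chance of passing at N = 4,000 is 0.9%, 4.5%, 16% and 66%.

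**Making OFF-without-FP patients non-evaluable.** In the same model this gives p / [1 − f(1 − 0.0823)]. At f = 15% that is 0.1483/0.8623 = 17.2%; at 20% and 30% it is 17.7% and 18.9%. The true value is 16%, so this option overstates the risk by as much as, or more than, the written rule understates it.

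**FPR.** If 10% of person-time is OFF, a true ON-time rate of 1.9/0.9 = 2.11 reads as 1.9. The cap of two counted FPs per patient limits the practical effect. If 15% of patients have an FP and the other 85% each contribute a full year, the counted rate is at most (2 × 0.15)/0.85 = 0.35 per patient-year, far below 1.9.

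**Sensitivity.** At 41 events, success needs 27 true positives (lower bound 50.5%; 26 gives 48.1%). If a share g of ACS events occurs while OFF, counted sensitivity is 0.70(1 − g), and power is P(Bin(41, ·) ≥ 27):

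| g | counted sensitivity | power |
|---|---|---|
| 0 | 70.0% | 0.776 |
| 5% | 66.5% | 0.606 |
| 10% | 63.0% | 0.420 |

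**The case against.** The strongest reply is that the documents are silent: nowhere do they say that OFF time counts. In 4.3.2 and 4.4.1 the ON condition stands beside completion of Baseline and could be read as continuing, and 4.3.3 does not define patient-years to include OFF time. A separate investigational protocol is cited in 4.7.10, the flow diagram is not shown, and much of the sample-size text is redacted; an allowance for switch-off may sit there. This stands in part. But 4.3.3 ties ON status to Baseline, and a continuing condition would itself need a rule for patients who lose it. The analysis rules that are visible contain none.

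Second, nuisance alarms may be the commonest reason for switch-off, and a patient switched OFF after an FP is already an FP patient. This is correct for the FP percentage: only OFF without a prior FP matters there. The run-in (3.1) is also meant to identify unsuitable patients before counting starts, which may keep such switch-offs few. It lowers the rate but supplies no rule.

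Third, the safety effect is modest away from the margin. At a true 16%, a probable wrong pass needs about 30% of patients OFF, which nothing in the documents suggests. This stands, as does the point that the FPR test is unlikely to turn on OFF time.

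A reader might also infer that both primary endpoints are distorted in the device's favour. The documents do not support that. The sensitivity effect runs against the device and cannot produce false success, and the existence and size of either bias depend on a switch-off rate that is not given. With no post-Baseline switch-off there is no bias.

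**Conclusion.** The concern holds as a missing rule whose literal default gives wrong answers once the feature is OFF. The safety measures are pulled toward success and sensitivity is pulled down.

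Under the stated assumptions, 5% to 10% of patients OFF at 6 months raises type I error at the 15% margin from about 0.02 to 0.04–0.08 (N = 1,000) or 0.09–0.24 (N = 4,000). If 5% to 10% of ACS events occur while OFF, power at 41 events and 70% sensitivity falls from 0.78 to 0.61–0.42. More than 41 events, or a higher true sensitivity, would soften the power loss.

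These figures illustrate what is possible and do not predict what will happen. The matter should be settled before analysis because the plan itself expects switch-off and because the safety error favours success.

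**What to change.** Define time at risk in the SAP as time with the feature programmed ON, then:

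- **(a) FP percentage.** Estimate the 12-month proportion by Kaplan-Meier time to first FP, censoring at switch-off and at loss to follow-up. Test its upper limit against 15%; section 4.3.1 already uses Kaplan-Meier with Greenwood's variance. Do not make OFF-without-FP patients non-evaluable, because that biases the percentage upward.
- **(b) FPR.** Count only ON time in patient-years.
- **(c) Sensitivity.** Report it for ACS events that occur while the feature is ON, always next to the as-written figure for all ACS events, since the restriction moves the estimate in the device's favour. State in advance which figure the 50% test uses.

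Keep the as-written analyses as supportive.

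The cost is mainly SAP wording, plus fewer events in (c). There are two limits. Switch-off may be informative, in which case censoring is not neutral, so the reasons for switch-off should be tabulated through month 12 and not only in the preliminary assessment. Section 4.7 shows status at each visit but not exact switch-off dates; if dates are unavailable, visit-level status must be used, with a stated convention for the interval between visits.
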